Specific Aim 3: We will develop the most appropriate anesthesia regimen for NET. In the past, NET has been delivered using the same anesthesia regimen as ECT. However, since no seizure is elicited with NET, the patient is likely to require only brief sedation rather than general anesthesia for the procedure (as is standard for ECT). Whereas it is typical during ECT to adjust the administered dose of anesthetic medications in subsequent treatments to minimize the time requiring ventilatory/circulatory support and post-ictal confusion, we will determine optimal dosing strategies for NET. We hypothesize that NET participants will require only minimal sedation without neuromuscular blockade.

Description of Subject Population

In this section, you are to describe each subject population of the study. The demographics of the population should reflect the gender and ethnic distribution of each population being studied. Enter each subject population's sample size, Gender, Racial, and Ethnic breakdown, and finally, describe each subject population.

Participants with Chronic Pain

Subject Population	Number of completers required to accomplish study aims	Projected number of subjects who will be enrolled to obtain required number of completers	Age range of subject population
Chronic pain patients	12	20	22-60

Gender, Racial, and Ethnic Breakdown:

We expect to enroll 50% women; 50% white, 25% black; 25% Hispanic/Latino

Description of subject population: Participants with refractory chronic pain with at least 3 months duration with a diagnosis of chronic postoperative pain, low back pain, musculoskeletal pain, fibromyalgia, visceral pain or neuropathic pain, including complex regional pain syndrome

Suicide Risk Management Plan

This section will include all information regarding the Suicide Risk Management Plan.

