- b) Clinical Global Impression (CGI) scale, a measure of symptom severity, treatment response and the efficacy of treatments as measured by a study physician (three days week).
- c) Beck Depression Inventory (BDI): the 21 item self-report rating scale for depression (weekly).
- d) Beck Anxiety Inventory (BAI): the 21 item self-report rating scale for anxiety (weekly).
- e) The Defense and Veterans Pain Rating Scale (DVPRS), a graphic tool that clinicians use to facilitate self-reported pain from patients, including the supplemental questions (weekly).

Subjects will be asked to confirm that they have had no food or drink for 8 hours with the exception of required prescription medication which they can take by mouth on the morning of the procedure with a small sip of water. They will then be asked to change into a hospital gown, escorted to the ECT suite. Vital signs (blood pressure, heart rate, and oxygen saturation) will be recorded at baseline and every 5 minutes through the end of the procedure. EEG leads will be placed in the middle of the forehead and on the left mastoid to monitor for any seizure activity. The EEG output will be reviewed to assess the absence of a seizure.

General anesthesia will be performed by an anesthesiologist. TEST will be sub-convulsive, but since seizure threshold determination for ECT involves sub-convulsive stimulation and is done routinely, there are no substantial differences or additional risks with TEST.

Protocol Summary Form

The absence of a seizure will be verified per usual ECT protocol by observing for tonic-clonic movements in a lower extremity isolated from neuromuscular blockade by a blood pressure cuff maintained above systolic blood pressure and with interpretation of the electroencephalogram (EEG) generated from the electrodes placed in the center of the forehead and one each on the left and right mastoid processes.

In the event that a subject has a seizure, the TEST dose will be lowered to 1/10th of the ECT dose (from 1/8th). The seizure will be discussed with the participant, including the plan to reduce the dose. If a participant has a seizure at 1/10th dose, they will be discontinued from the study.

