This protocol consists of an early feasibility study. Thus, all participants will receive active stimulation (no sham group) using an open-label design enrolling 12 participants. We have chosen this sample size in order to assess the following outcome measures: willingness to participate, tolerability, cognition, and pain. The willingness to participate will be assessed by measuring the percentage of participants who enroll out of those who are screened for the study. We expect that at least 20% will agree to enroll.

Criteria for Early Discontinuation

Define criteria that will be used to exit or drop subjects from the study and operationalize. Indicate the time points when such criteria will be applied, and describe the rating instruments, parameters, and thresholds that will lead to a decision

Protocol Summary Form

to terminate a subject's participation and the role of the person who will make these determinations. Studies which include a medication taper and discontinuation may be asked to include an independent medical monitor (an MD not on the study team) who will aid the study team in determining whether study discontinuation is needed. In addition, explain procedures for managing subjects who are withdrawn from the protocol.

For treatment studies: To minimize risks to subjects, operationalized drop-out criteria should be defined so that subjects who worsen, or in some cases, fail to improve, are removed from the study and offered standard care. The threshold for drop-out should consider the level of risk associated with non-improvement for the specific disorder, the availability of alternatives, and the typical required duration of treatment. For example, emergence of suicidal intent, or psychosis, should prompt immediate clinical evaluation and withdrawal from the study.

Participants will be discontinued if they have two seizures. In the event that they have one seizure the TEST dose will be lowered to 1/10th of the standard ECT dose (from 1/8th). The seizure will be discussed with the participant, including the plan to reduce the dose. If a participant decides to continue, this will be documented in their chart. If a participant has a seizure at 1/10th dose, they will be discontinued from the study.

Blood and other Biological Samples

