Risks of TEST: Previous experience with TEST is limited to patients with major depression, as described by Regenold et al, 2015. In this publication, TEST was delivered at 1/8th (which is the same as 1/16th age) the usual ECT dose for 7 seconds. Please note that a sister study is currently being performed at NIMH (in collaboration with our group here at NYSPI) by [name] using these same parameters. This protocol will use the same parameters as those used by Regenold et al (2015), as delineated in the procedures section.

Although not intended, a seizure is possible with the delivery of TEST. We do not expect a seizure to occur, as we are using the lower dose of TEST (reported in Regenold et al, 2015). If a seizure occurs, the subject will be monitored as though they have received ECT. Following this session, they will be informed of the seizure and asked if they would like to be removed from the protocol or continue. If they chose to continue, the dose will be lowered by 25%. If another seizure is elicited, they will be monitored appropriately and then removed from the protocol. Based on the previous publication by Regenold et al (2015) we do not expect a seizure to occur. Nonetheless, participants will be informed of this possibility and the need to stop the study.

The anesthesia medications include glycopyrrolate, methohexitol sodium, and succinylcholine. The risks of glycopyrrolate include anti-cholinergic effects (dilated pupils, increased body temperature, fast or irregular heart rate, blurred vision, constipation, drowsiness, dry eyes, dry mouth, flushing, and light sensitivity). The risks of methohexitol sodium include drowsiness, nausea, vomiting, stomach pain, chills or shivering, coughing, hiccups, muscle twitching, or mild skin rash or itching. The side effects of succinylcholine include jaw rigidity, hypotension, muscle fasciculation, respiratory depression, and salivary gland enlargement. Rare side effects include a severe allergic reaction, malignant hyperthermia, transient residual weakness due to prolonged succinylcholine activity (due to pseudocholinesterase deficiency, which is exceedingly rare [approximately 1 per 2000 to 5000 people] but would make succinylcholine last longer than 3-5 min), myoglobinuria/myoglobinemia, and arrhythmias.

Other risks of TEST include:

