of these. In addition, we inform volunteers that we must conform with NY State reporting requirements (e.g., child abuse). In addition to a discussion of this topic, the information is clearly stated in our consent forms. Participants in other studies have understood this and have agreed to participate under these conditions.

We are collaborating with the lab of [name], at the Medical University of South Carolina, who will model the electrical field generated by TEST. To accomplish this, MRI scans will be sent to MUSC. The MRI scan files do not contain PHI and the scan itself is not considered PHI (per [name], director of the MRI core. The consent form makes this clear to participants. It also says that participants are not required to agree to have their MRI shared in order to participate. In this case, a note will be included in their file and the MRI will not be sent.

Some participants completed the study prior to this collaboration. Thus, I will call these three participants to discuss the option of allowing us to share their MRI scans. If they agree, consent will be obtained either through RedCap or by mailing a consent form addendum (along with a return envelope).

Will the study be conducted under a certificate of confidentiality?

- Yes, we will apply for the Certificate of Confidentiality
- Yes, we have already received a Certificate of Confidentiality
- No

Direct Benefits to Subjects

Describe only benefits to individual subjects that are likely to accrue during the study itself. Do not include subject compensation or treatment to be provided at the end of the study, as these do not figure into the IRB's risk/benefit considerations. Do not describe diagnostic and evaluation components unless subjects receive clinical feedback. Do not describe the anticipated scientific benefits of the research. Some studies offer no direct benefit to subjects.

This study is not designed to benefit participants directly

Compensation and/or Reimbursement

If compensation or reimbursement for expenses will be offered to subjects, please describe and indicate total amount and schedule of payment(s). If transportation is reimbursed, state if receipts are necessary for reimbursement. Include justification for compensation amounts and indicate if there are bonus payments.

Data Management Plan

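### The dose after a first seizure is stated two ways: 1/10 of the ECT dose in the procedures and discontinuation criteria, a 25% cut (3/32) in the risks section

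*Combined protocol and SAP*

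**What the plan says.** The starting dose comes from the earlier depression study. Under Risks/Discomforts/Inconveniences, the paragraph on TEST risks says that in that study "TEST was delivered at 1/8th (which is the same as 1/16th age) the usual ECT dose for 7 seconds", and that this protocol uses the same parameters.

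Three places then say what happens if a participant has a seizure:

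- **Study procedures, TEST sessions:** "In the event that a subject has a seizure, the TEST dose will be lowered to 1/10th of the ECT dose (from 1/8th" (closing bracket omitted).
- **Criteria for Early Discontinuation:** "In the event that they have one seizure the TEST dose will be lowered to 1/10th of the standard ECT dose (from 1/8th" (closing bracket omitted).
- **Risks/Discomforts/Inconveniences, risks of TEST:** "If they chose to continue, the dose will be lowered by 25" per cent.

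The stop rules also differ in form. The procedures and the discontinuation criteria both say "If a participant has a seizure at 1/10th dose, they will be discontinued from the study". The discontinuation criteria add that two seizures end participation. The risks paragraph removes a participant after a second seizure and does not name the dose at which it occurs.

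**The concern.** All three statements are current text, and each tells staff what to do at the same moment. A clinician working from the risks paragraph would set a different dose from one working from the procedures. Whichever is followed, the treatment departs from another section of the approved protocol.

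The stop rule is affected too. In the procedures, the only exit rule for seizures is tied to the 1/10 dose. A participant whose dose was cut by 25% is never treated at 1/10, so that rule, read literally, does not apply to that person. Cover then comes from the two-seizure rule in the discontinuation criteria and the second-seizure rule in the risks paragraph.

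The study is also under way. Under Methods to Protect Confidentiality, some participants are said to have finished before the MRI-sharing collaboration began: "Thus, I will call these three participants to discuss the option of allowing us to share their MRI scans". The conflicting instruction may therefore already have been in force when people were treated.

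**Working it through.** **Inputs.** Start: 1/8 of the ECT dose (all three places). Step-down A: to 1/10 (procedures; discontinuation criteria). Step-down B: a 25% cut (risks paragraph). Age range: 22 to 60 (Description of Subject Population). Age equivalence: 1/8 of the ECT dose equals age/16 (risks paragraph).

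**Step 1: each rule from the same start.**

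- A: 1/10 = 0.100. Size of cut: 1 − (1/10)/(1/8) = 1 − 0.8 = 20%.
- B: (1/8) × (1 − 0.25) = 3/32 = 0.09375, about 1/10.67. Size of cut: 25%.
- Gap: 0.100 − 0.09375 = 0.00625 of the ECT dose. Relative to A: 0.00625/0.100 = 6.25%.

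**Step 2: can the two be reconciled?** For 1/10 to be a 25% cut, the start would have to be 0.100/0.75 = 0.133, or 1/7.5. No such starting dose appears. Moving to the age scale does not help, because a percentage cut is the same on any proportional scale. One possible source of the 25% is a change of base: (0.125 − 0.100)/0.100 = 25%, so 1/8 is 25% above 1/10. That is a guess about how the figure arose. Lowering a dose by 25% ordinarily means 25% of the dose being lowered.

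**Step 3: the same doses on the age scale.** If 1/8 of the ECT dose is age/16, the full dose is age/2, 1/10 of it is age/20, and the 25% cut is (3/4) × age/16 = 3 × age/64.

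| Age | Start (age/16) | A (age/20) | B (3 × age/64) | A − B |
|---|---|---|---|---|
| 22 | 1.375 | 1.100 | 1.031 | 0.069 |
| 60 | 3.750 | 3.000 | 2.8125 | 0.1875 |

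**Step 4: stop rules under each dose.**

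| Rule | Participant stepped down to 1/10 | Participant cut by 25% |
|---|---|---|
| Seizure at 1/10 (procedures; discontinuation criteria) | Applies | Never triggered as worded |
| Two seizures (discontinuation criteria) | Applies | Applies |
| Second seizure (risks paragraph) | Applies | Applies |

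Everyone is removed after a second seizure. Only the rule tied to 1/10 fails to match the 25% version.

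**The case against.** The strongest reply is that this matters little in practice. The two sections that direct conduct agree on 1/10, and the outlier is one sentence in a risk narrative. Both versions lower the dose, the gap is 6.25% of the 1/10 dose, and a second seizure ends participation either way. Any seizure would occur under general anesthesia with EEG recording and be monitored as after ECT. All of that stands, and it is why the point is minor. It does not remove the conflict, because the risks sentence is also worded as an instruction.

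It can also be said that choosing 1/10 takes the higher of the two doses by majority, with no clinical argument. That is fair. The documents do not show which value the team intends, so the fix leaves the choice open.

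A reader might go further and infer that the plan is deficient because no visible rule acts across participants, so that later participants start at 1/8 even if several earlier ones had seizures. It is true that every visible seizure rule acts within one participant, but the documents do not support calling this a defect:

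- The discontinuation section is a form field for individual exits, so a study-level rule would not be expected there.
- The device has an approved IDE, and a rule could sit in that file or in other material not shown.
- The study is open-label and staff check for a seizure at each session. The risks paragraph also notes that "a sister study is currently being performed at NIMH (in collaboration with our group here at NYSPI" (closing bracket omitted). Nothing prevents the team from acting on accumulating events.
- No seizure rate is given, so a preset count cannot be justified from the documents. With assumed per-participant risks from 5% to 30%, the chance that at least 2 of 12 participants have a seizure, 1 − (1 − p)^12 − 12p(1 − p)^11, runs from 12% to 91%.
- Starting later participants at 1/10 would mix doses within 12 people, depart from the stated intent to keep the earlier study's parameters, and remove those participants after one seizure under the 1/10 stop rule.

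A study-wide trigger is therefore a debatable trade-off and at most an optional addition.

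**Conclusion.** The point holds as an inconsistency in an operative dose: 0.100 of the ECT dose in two sections and 0.09375 in a third, with no stated starting dose that reconciles them. It is wrong as written and minor. The result is exact arithmetic and assumes only that the percentage cut is taken from the 1/8 starting dose.

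It would be too strong to say that either dose is unsafe, or that a participant could go on having seizures without a stop rule. The documents give no seizure rate at 1/8, 1/10 or 3/32, and the two-seizure rule covers both versions. The visible text does not give the device's dose increments either, so whether it can deliver both values is unknown. That does not affect the need for one stated value.

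**What to change.** In the risks paragraph, replace the 25% reduction with a step from one eighth to one tenth of the ECT dose, as in the procedures and the discontinuation criteria. This changes one phrase and leaves the stop rule at 1/10 correct.

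If the team intends the 25% cut, keep the risks sentence and change four sentences elsewhere: the dose and the stop rule in the procedures, and the same pair in the discontinuation criteria, each to 3/32 of the ECT dose.

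Either route needs one amendment and no new procedure, data item or change in sample size. Before submitting it, check whether any participant already treated was stepped down and record the dose given. Optionally, if the IDE or IRB file already has a rule on accumulating seizures, add a one-line reference to it.

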This is a preliminary, open label feasibility study in adults with CNCP. Subjects will be recruited from the pain clinics of Columbia University Irving Medical Center. Given that this is a feasibility study, it is open to participants with chronic pain caused by a wide range of disorders. Please note that chronic pain, independent of the original etiology, has been shown to involve the medial prefrontal cortex and cingulate. Thus, in this pilot study, the procedure is open to patients with different primary causes of pain who suffer with chronic pain. Subjects will be admitted to the research unit at NYSPI. They will receive three treatments weekly for a total of 8-9 treatments, using the dosing from the previous study of refractory depression (Regenold et al, 2015). Ratings of pain, mood, and memory will be obtained before and after the TEST sessions, and weekly for 4 weeks after the end of the TEST sessions.

Specific Aims and Hypotheses

Concisely state the objectives of the study and the hypothesis or primary research question(s) being examined. There should be one hypothesis for every major study procedure or intervention. For pilot studies, it is important not to overstate the study's objectives. If there are no study hypotheses, describe broad study goals/aims.

Specific Aim 1: We will determine the feasibility of administering NET to participants with chronic pain. Like ECT, NET will be delivered three days a week for three weeks (for a total of 8 to 9 sessions). We will recruit 6 subjects with a diagnosis of chronic pain, defined as pain lasting more than 6 months, that has not remitted with pharmacotherapy, with no other known treatment (examples include chronic postoperative pain, low back pain, musculoskeletal pain, fibromyalgia, visceral pain and neuropathic pain, including complex regional pain syndrome). Our hypothesis is that NET will prove to be safe and tolerable in this patient population and will show preliminary efficacy, defined a priori as a decrease in pain of at least 30%.

Specific Aim 2: We will determine the preliminary efficacy in 6 patients with chronic pain (using the same criteria as above) who have comorbid major depression. We will use the same inclusion criteria and the same outcome measures as Aim 1, obtained before and after the NET sessions. Our hypothesis is that NET will be safe, tolerable, and will have preliminary efficacy on symptoms of major depression in addition to chronic pain (improvement of at least 30%).

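### The seizure exit rule does not separate stopping TEST from leaving the study, so a participant who exits may miss the only listed post-baseline cognitive battery

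*Combined protocol and SAP*

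**What the plan says.** The exit rule appears in three places in the combined protocol and SAP.

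- **Study procedures narrative and Criteria for Early Discontinuation.** Both say: "If a participant has a seizure at 1/10th dose, they will be discontinued from the study". The second section also says: "Participants will be discontinued if they have two seizures". That sentence does not say what is discontinued.
- **Risks/Discomforts/Inconveniences, after a second seizure:** "If another seizure is elicited, they will be monitored appropriately and then removed from the protocol".
- **Risks/Discomforts/Inconveniences, after a first seizure:** "Following this session, they will be informed of the seizure and asked if they would like to be removed from the protocol or continue". The section adds that "participants will be informed of this possibility and the need to stop the study".

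The five cognitive instruments (AMI-SF, Trail Making, Stroop, RBANS, MoCA) are given on the baseline scan day. They are listed once more, when the TEST sessions end and before discharge from the unit. The assessments listed during the course are BPI, CGI, BDI, BAI and DVPRS. The weekly telephone follow-up lists TLFB, BPI, BDI, BAI and medication changes.

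Analysis and Outcomes names cognition as one of four outcome measures.

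**The concern.** Stopping an intervention and stopping data collection are different decisions, and the exit wording merges them. After a first seizure the participant is offered removal or continuation. Stopping TEST while remaining for assessment is not offered. The form's own prompt under Criteria for Early Discontinuation asks how withdrawn subjects will be managed. The response gives the trigger and the dose reduction, but no procedure after exit.

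The data at risk bear on a central question. The Lay Summary contrasts TEST with ECT on memory effects, and the Risks section lists short-term memory loss and difficulty learning. After a seizure, "the subject will be monitored as though they have received ECT". A participant who has seized has therefore had something closer to ECT than the intended exposure, and is plausibly at higher cognitive risk than one who has not. A rule that may leave these people untested loses cognitive data selectively. A reassuring memory result could then rest on the participants least likely to show a problem.

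**Working it through.** The plan gives no figure for this point, so the check is mainly a comparison of the text, followed by simple arithmetic on size.

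**Step 1. Who exits.** There are two routes: a second seizure (mandatory exit) and a first seizure followed by the participant's choice to leave. A participant who has one seizure and continues at the lower dose is not affected.

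**Step 2. What cognitive data such a person has under a literal reading.**

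| Time | Cognitive tests listed | Obtained if the person leaves the study at exit? |
|---|---|---|
| Screening | MMSE | Yes |
| Baseline scan day | AMI-SF, Trail Making, Stroop, RBANS, MoCA | Yes |
| During the TEST course | None | Not applicable |
| End of TEST, before unit discharge | AMI-SF, Trail Making, Stroop, RBANS, MoCA | Uncertain |
| Weekly calls for a month | None in the legible list | Not applicable |

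If the end-of-course row is missed, no listed instrument yields a change from baseline.

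**Step 3. Could it be recovered later?** The Background section says: "Ratings of pain, mood, and memory will be obtained before and after the TEST sessions, and weekly for 4 weeks after the end" of the sessions. That would include memory, but the telephone list names no cognitive test. The last follow-up sentence in the study procedures breaks off where assessments would be named. Later recovery is therefore unknown, and the cut-off is not held against the plan.

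**Step 4. Size per person.** The input is 12 participants (Analysis and Outcomes; Description of Subject Population).

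- One exit, not replaced: 1/12 = 8.3% of the cognition data set.
- One exit, replaced, so that 13 are treated: 1/13 = 7.7%.
- Two exits: 2/12 = 16.7%, or 2/14 = 14.3% if both are replaced.

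**Step 5. Precision against selection.** Suppose no decline is seen in anyone tested. The one-sided 95% upper bound on the decline rate is 1 − 0.05^(1/n). For n = 12 it is 22.1%, and for n = 11 it is 23.8%. One missing person barely changes precision. If that untested person did decline, however, the true count is 1 of 12 (8.3%) while the reported count is 0 of 11. The issue is who is missing, not how many.

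**Step 6. How often.** The documents give no exit rate, so this range is an assumption. With a per-participant exit probability p among 12:

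- P(at least one exit) = 1 − (1 − p)^12. This is 11% for p = 1%, 46% for p = 5% and 72% for p = 10%.
- P(none or one) = (1 − p)^12 + 12p(1 − p)^11. This is 99%, 88% and 66% for the same values.

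The plan does not expect seizures, which points to the low end.

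**The case against.** The strongest reply is that the existing text already covers the case. The battery is triggered by the end of the TEST sessions and by discharge from the unit, not by completing 8 or 9 sessions. Participants are inpatients, so someone who stops after a seizure has reached the end of their sessions and must still be discharged. The study procedures also describe four weeks of calls and assessments after discharge from the study, so leaving the study need not end data collection. Part of the document around the consent section is not in the copy reviewed, and withdrawal handling could be there.

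This reading is fair, and it makes the loss possible rather than certain. It does not close the gap, because no available sentence says that a participant who exits after a seizure is tested, and the exit wording points the other way.

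It is also true that the trigger is narrow. Mandatory exit needs a second seizure, at a reduced dose of a stimulus chosen to be sub-convulsive. Seizures are still recorded by EEG and observation, and adverse events are followed by a study physician until they resolve. A reader might infer that participants are abandoned clinically after exit. The documents do not support that; the gap is in cognitive measurement.

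A reader might also infer a biased completer analysis from the table in Description of Subject Population, which sets 12 completers against 20 under "Projected number of subjects who will be enrolled to obtain required number of completers". That heading belongs to a recruitment table. No completer analysis is defined anywhere, and the 8 extra enrolments allow for non-completion of any kind, not for seizures.

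**Conclusion.** The point stands as a minor one. Taken literally, the exit rule can remove a participant before the only cognitive battery listed by instrument after baseline, and it would do so for people whose memory results matter most to the comparison with ECT.

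The number affected is probably zero or one. Each such person is about 8% of a 12-person cognition data set. This rests on three things: the exit wording is followed as written, the battery is not given at early discharge, and no cognitive test sits in the text that is missing or cut off. The higher cognitive risk of those who seize is plausible from the plan's own handling of them, but the documents do not quantify it. No size of bias in the cognition results can be derived, because neither the number of exits nor their cognitive change is known.

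**What to change.** In the study procedures, Criteria for Early Discontinuation and Risks sections, replace the study-exit and protocol-removal wording with a single rule:

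- A seizure exit, whether mandatory or chosen, ends TEST sessions only.
- Unless consent is withdrawn, the participant completes the existing end-of-course battery before leaving the unit, and then the weekly calls.
- The participant is included in the cognition summary, with the number of sessions received reported, since a partial course is not the same exposure as a full one.

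The seizure thresholds for stopping TEST stay as they are.

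The cost is low: one amendment to the protocol, with matching consent wording. No new instrument or visit is needed, because these participants are already inpatients with the battery scheduled. The downside is a modest assessment burden on people who stop early, some of whom may decline.
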